Appendix B Eastern Cooperative Oncology Group Response Criteria

Complete Response	Clinical: Complete disappearance of all clinically detectable malignant disease Pathologic: Pathologic proof of a clinically complete response after repeat biopsy of areas of known malignant disease
Partial Response	≥50% decrease in tumor area, without increase in size of any area of known malignant disease of >25% or appearance of new areas of malignant disease
Stable Disease	No significant change in measurable or evaluable disease: 
• No increase in size of any known malignant disease• No appearance of new areas of malignant disease• This designation includes
- Decrease in tumor area in the sum of products of the individual lesions of <50%OR- Decrease in uni-dimensional measurable disease of <30%OR- Increase in malignant disease of <25% in any site• No deterioration in ECOG performance status of ≥1 level related to malignant disease
Progressive Disease	
• Significant increase in size of lesions present at the start of therapy or after a response
- ≥25% in the area of any malignant lesions >2 cm² or in the sum of products of the individual lesions, or- ≥50% in the area if only one lesion is measurable and was ≤2 cm² at the initiation of therapy OR 
• Appearance of new metastatic lesions known not to be present at the start of therapy OR 
• Stable objective disease associated with deterioration in ECOG performance status of ≥1 level related to malignancy

Source: Oken MM, Creech RH, Tormey DC, Horton J, Davis TE, McFadden ET, et al. Toxicity And Response Criteria Of The Eastern Cooperative Oncology Group. Am J Clin Oncol. 1982;5(6):649-55

Appendix C Preoperative Endocrine Prognostic Index (PEPI)

Pathology, biomarker status	Relapse-Free Survival (RFS)	Breast Cancer-Specific Survival (BCSS)
Pathological tumor size		
T1/2	0	0
T3/4	3	3
Node status		
Negative	0	0
Positive	3	3
Ki67		
0%-2.7% (0-1*)	0	0
>2.7%-7.3% (1-2*)	1	1
>7.3%-19.7% (2-3*)	1	2
>19.7%-53.1% (3-4*)	2	3
>53.1% (>4*)	3	3
ER status, H-score score		
0-2	3	3
3-8	0	0

* The natural logarithm interval corresponding to the percent Ki67 values on the original percentage scale

Source: Matthew J. Ellis, Yu Tao, Jingqin Luo, et al. Outcome Prediction for Estrogen Receptor – Positive Breast Cancer Based on Postneoadjuvant Endocrine Therapy Tumor Characteristics. J Natl Cancer Inst. 2008;100:1380-8.

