8.1.3 Preoperative Endocrine Prognostic Index (PEPI)

PEPI score will be assessed after a 14-day treatment period. The assessment includes relapse-free survival (RFS) risk score and breast cancer specific survival (BCSS) risk score.

The total PEPI score is the sum of the risk points derived from the pathological tumor (pT) stage, the pathological node (pN) stage, Ki67 levels and ER status (Allred score) of the surgical specimen. The pT and pN will be assessed locally. The Ki67 and ER status will be assessed centrally.

See Appendix 12 ([Section 10.12](#)) for details.

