10.12 APPENDIX 12: PREOPERATIVE ENDOCRINE PROGNOSTIC INDEX

Table 16 - Preoperative endocrine prognostic index (PEPI)

Pathology, biomarker status	Relapse-Free Survival (RFS)	Breast Cancer-Specific Survival (BCSS)
Pathological tumor size		
T1/2	0	0
T3/4	3	3
Node status		
Negative	0	0
Positive	3	3
Ki67		
0%-2.7% (0-1*)	0	0
>2.7%-7.3% (1-2*)	1	1
>7.3%-19.7% (2-3*)	1	2
>19.7%-53.1% (3-4*)	2	3
>53.1% (>4*)	3	3
ER status, Allred score		
0-2	3	3
3-8	0	0

* The natural logarithm interval corresponding to the percent Ki67 values on the original percentage scale

Source: Matthew J. Ellis, Yu Tao, Jingqin Luo, et al. Outcome Prediction for Estrogen Receptor – Positive Breast Cancer Based on Postneoadjuvant Endocrine Therapy Tumor Characteristics. J Natl Cancer Inst. 2008;100:1380-8.

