2.1.3.3 Additional endpoint(s)

- ECOG response rate is defined as clinical complete response (cCR), pathological complete response (pCR) or partial response (PR), as measured by ultrasound according to ECOG response criteria (see [Appendix B](#)). The ECOG response (except pCR) will be assessed by investigator and collected in CRF.
- The proportion of participants achieving pCR after a 14-day treatment period. The pCR will be assessed by investigator and collected in CRF.
- PEPI risk score is the sum of the risk points derived from the pT stage, the pN stage, Ki67 levels and ER status of the surgical regimen. It will be calculated with the rules as defined in [Appendix C](#). PEPI score will be calculated for both RFS and BCSS based scale.
- Complete cell cycle arrest (CCCA) is a marker of reduced cellular proliferation, is defined as a Ki67 $\leq 2.7\%$ at D15 on central assessment.
- The proportion of participants with post-treatment Ki67 $< 10\%$.
- Additional protein expression assessments (eg, Ki67) by using digital image-based method.

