2.4.5.1.2 Subgroup analyses

Evaluation of consistency

The consistency of the results from the primary analysis will be evaluated across pre-defined subgroups in patients available in the subgroup of consideration. The subgroups included but not limited are defined in [Table 4](#). Depending upon the study results, additional subgroups may be examined, and subgroups with small sample sizes may be pooled to create a larger meaningful subgroup. For each subgroup, geometric LS-mean of percentage reduction in Ki67 with their associated 95% CIs and geometric LS-mean ratio of proportional change between treatment arms with their associated 95% CIs will be provided for each treatment arm.

Evaluation of interactions

For each pre-defined factor defined in [Table 4](#), log-fold change in Ki67 will be analyzed using linear regression model with terms for the factor, treatment and their interaction, adjusted by log baseline Ki67. The p-value of the test of interaction will be provided.

Other prognostic factors

Since the results from the primary analysis could be impacted by confounding factors, any potential issues will be examined and, if confirmed, exploratory analysis of the primary endpoint will be done accordingly. A multiple linear regression model will be used to identify prognostic factors among the demographic and baseline characteristics factors described in the [Table 4](#) using a stepwise selection procedure with a 15% significance level for removing effects. For significant prognostic factors identified in the multivariate model, the balance between treatment groups will be assessed.

Table 4 - Subgroup analyses

Prognostic factor	Description
Age	<65 years or ≥65 years
Race	Asian or White or Other
Tumor stage	1 or 2 or ≥ 3
Tumor size (greatest dimension)	≥10 mm to < 20mm, ≥ 20mm
Ki67 level at baseline (per central assessment)	<20% or ≥20%
ER H-score at baseline	Low ER+. (H-score 1-100) or moderate ER+ (H-score 101-200) or high ER+ (H-score 201-300).
Progesterone receptor	< 20% vs ≥20%

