2.4.5.3 Additional analyses

Clinical response rate

ECOG response rate on each arm will be estimated by dividing the number of participants with clinical response (defined as clinical complete response (cCR), pathological complete response (pCR) or partial response (PR) as measured by ultrasound according to ECOG response criteria) by the number of participants from analysis population of the respective treatment arm. In addition, 95% two-sided CIs will be computed using the Clopper-Pearson method.

pCR rate

Pathological complete response rate on each randomized arm will be estimated by dividing the number of participants with complete pathological response (ie, no histologic evidence of invasive tumor cells in the surgical breast specimen and axillary nodes identified after neoadjuvant treatment) by the number of participants from the analysis population of the respective treatment arm. In addition, 95% two-sided CIs will be computed using the Clopper-Pearson method.

PEPI risk score

The total PEPI score, as defined in [Section 2.1.3.3](#), is the sum of the risk points derived from the pT stage, the pN stage, Ki67 levels and ER status of the surgical regimen. The total score after treatment will be summarized (quantitatively and by 3 risk categories: 0 (low risk), 1-3 (medium risk) and ≥ 4 (high risk)) for each treatment arm.

Complete cell cycle arrest (CCCA)

The proportion of participants with CCCA will be provided for each treatment arm along with the 95% CI computed using the Clopper-Pearson method.

Post-treatment Ki67 <10%

The proportion of participants with post-treatment Ki67 <10% will be provided for each treatment arm along with the 95% CI computed using the Clopper-Pearson method.

Ki67 by digital image-based method

The primary analysis defined in [Section 2.4.5.1.1](#) (except for ICC) will be performed on Ki67 results by digital image-based method.

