2.5.3 Missing data

The analyses and summaries of continuous and categorical variables will be based on observed data only. Percentages will be calculated using as denominator the number of patients with non-missing observation in the considered population. When relevant, the number of patients with missing data is presented.

Handling of disease characteristics missing/partial dates

- If the day is missing, it will be imputed by 1.
- If the month is missing, it will be imputed by 1 (only for medical history variables).
- If the year is missing, no imputation will be performed.

Incomplete date of cancer diagnosis:

- If the day of the cancer diagnosis is missing, the date will be imputed to the first day of the month.
- If day and month of the cancer diagnosis are missing, no imputation will be done.

Handling of medication missing/partial dates

No imputation of medication (other than anti-cancer therapies) start/end dates or times will be performed. If a medication date or time is missing or partially missing and it cannot be determined whether it was taken prior or concomitantly, it will be considered a prior and concomitant medication.

Imputation of incomplete date for post anti-cancer treatment start date

For post anti-cancer treatments, if the medication start date is missing, it will be imputed as follows:

- If the medication start day and month are missing and the medication start year is the same as treatment end year, the medication start date will be set equal to treatment end date +1.
- If the medication start day and month are missing and the medication start year is after the treatment end year, the medication start day and month will each be set to 01.
- If the medication start day is missing and medication start year and month is the same as the treatment end year and month, the medication start date will be set to the treatment end date +1.
- If the medication start day is missing and medication start month is before the treatment end month and the medication start year is the same as treatment end year, the medication start day will be set to 01.
- If the medication start day is missing and the medication start month is after the treatment end month and the medication start year is the same as treatment end year, the medication start day will be set to 01.

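### SAP Appendix C labels the PEPI ER item as H-score but keeps the Allred bands 0-2 and 3-8, so as written the exploratory PEPI total is undefined for any post-treatment H-score above 8

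*SAP*

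**What the plan says.** Protocol 8.1.3 builds the PEPI total from pathological tumour stage, nodal stage, "Ki67 levels and ER status (Allred score) of the surgical specimen", and adds that "The Ki67 and ER status will be assessed centrally". Protocol Table 16 (Appendix 12) heads the corresponding row "ER status, Allred score" and gives 3 points for 0-2 and 0 points for 3-8, on both the relapse-free survival (RFS) and breast cancer-specific survival (BCSS) scales.

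SAP Appendix C reproduces the table with the same bands, the same points and the same source, but its row heading is "ER status, H-score score". SAP 2.1.3.3 says of the PEPI score: "It will be calculated with the rules as defined in" Appendix C. SAP 2.1.3.3 and 2.4.5.3 speak only of ER status, and Allred is not named anywhere in the SAP.

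SAP 2.4.5.3 summarises the total by arm, as a quantity and in three risk categories: 0, 1-3, and 4 or more. For the H-score itself, SAP Table 4 (section 2.4.5.1.2) uses three classes: 1-100, 101-200 and 201-300.

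**The concern.** The row heading and the bands belong to different scales. Bands that stop at 8 cannot score a measure that the same SAP runs to 300. Because Appendix C is the SAP's scoring rule and the total is a sum of four items, a patient with a post-treatment H-score of 9 or more has no ER points and therefore no total.

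SAP 2.5.3 works from observed data and calculates percentages "using as denominator the number of patients with non-missing observation". Applied literally, the risk-category table would then contain only patients with an H-score of 8 or below, that is, those with almost complete loss of ER staining. ER degradation is the stated mechanism of amcenestrant, so this selection could differ between arms.

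The wrong label also matches a variable that will be in the dataset, because change in ER H-score is a secondary endpoint. A programmer following Appendix C would find a column with the stated name. One might leave most totals missing, another might give 0 points to every H-score of 3 or more, and a third might go back to the protocol. The SAP should allow only one of these.

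**Working it through.** The plan states no figure on this point to reproduce. The check applies the Appendix C rule to the scale it names.

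**Inputs**
- ER bands and points: 0-2 = 3 points, 3-8 = 0 points (SAP Appendix C; identical in protocol Table 16).
- H-score classes: 1-100, 101-200, 201-300 (SAP Table 4). Zero is added as the floor of the scale.
- Risk categories: 0, 1-3, ≥4 (SAP 2.4.5.3).
- Points for the other items (Appendix C): tumour T1/2 = 0, T3/4 = 3; nodes negative = 0, positive = 3; Ki67 in five bands = 0, 1, 1, 2, 3 for RFS and 0, 1, 2, 3, 3 for BCSS.

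**Step 1: coverage of the scale.** There are 301 integers from 0 to 300. The bands cover 3 (0 to 2) plus 6 (3 to 8), which is 9. Unscored: 301 − 9 = 292, and 292/301 = 97.0%. By SAP class, 8 of 100 values are scored in the low class, 0 of 100 in the moderate class and 0 of 100 in the high class.

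**Step 2: fall in H-score needed to be scorable.** A baseline B must end at 8 or below, so the required relative fall is 1 − 8/B.

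| Baseline H-score | Required fall |
|---|---|
| 101 | 1 − 8/101 = 92.1% |
| 201 | 1 − 8/201 = 96.0% |
| 300 | 1 − 8/300 = 97.3% |

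**Step 3: range by assumed fall.** The documents give no distribution, so this counts integer baselines that end at 8 or below under a uniform fall. The largest such baseline is 8/(1 − fall).

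| Assumed fall | Largest scorable baseline | Of the 200 baselines 101-300 | Of the 300 baselines 1-300 |
|---|---|---|---|
| 50% | 16 | 0 | 16 |
| 90% | 80 | 0 | 80 |
| 95% | 160 | 60 | 160 |
| 98% | 400 | 200 | 300 |

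These are counts of scale values with equal weight, not estimates of patient numbers.

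**Step 4: does the ER item matter to the category?** There are 2 × 2 × 5 = 20 combinations of tumour, node and Ki67. The category differs between 0 and 3 ER points whenever the subtotal without ER is 3 or less.
- T1/2, node-negative: RFS subtotals 0, 1, 1, 2, 3 and BCSS subtotals 0, 1, 2, 3, 3. All 5 change category.
- T1/2, node-positive: subtotal 3 plus Ki67 points. Only the lowest Ki67 band changes: 1.
- T3/4, node-negative: likewise 1.
- T3/4, node-positive: subtotal at least 6, always high risk: 0.

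Total: 5 + 1 + 1 + 0 = 7 of 20 on each scale. The other 13 are high risk with either ER value, although their numeric total still lacks its ER item.

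**Step 5: the same bands under the protocol's scale.** Read as Allred, 0-2 and 3-8 cover every integer from 0 to 8 with no gap, and every patient with an ER score receives 3 or 0 points.

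**The case against.** The strongest reply is that this is a one-word slip with an obvious remedy. The bands, points and source match protocol Table 16, and the SAP's list of changes records no change to PEPI scoring. SAP 1.4 also refers to protocol section 1.3 for assessment details, and the PEPI row there leads to protocol 8.1.3 and so to Allred. An error that empties most of a table would probably be noticed before release. SAP 2.5.3 is about missing observations; a recorded H-score with no matching band is a gap in the specification, so the emptied table is an inference. The baseline range 101-300 leaves out the low class, which is eligible because entry needs only 1% ER staining. PEPI is exploratory, with no between-arm test.

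Much of this is fair. The cross-reference confirms that Allred is the intended scale, but it does not override Appendix C, which remains the stated calculation rule. The emptied table is the result of a literal reading, not a prediction. Including the low class raises the counts (second range in Step 3) but leaves the gap above 8 untouched. Exploratory status limits the consequence; it does not make the rule correct. The doubt about laboratory reporting is only a query, since the protocol implies a central Allred reading, but it is reasonable because the SAP's central ER analysis names only H-score.

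**Conclusion.** The concern holds. The SAP's operative scoring table names the wrong scale for the PEPI ER item and contradicts the protocol. On a literal reading, 292 of 301 integer H-scores (97%) have no ER points, and the ER item decides the risk category in 7 of 20 tumour, node and Ki67 combinations on both PEPI scales, including all five that are T1/2 node-negative.

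The scale count assumes integer H-scores from 0 to 300. How many patients would be affected depends on post-treatment H-scores, which the documents do not give. The consequence is confined to the exploratory PEPI summaries; the primary Ki67 analysis, the secondary analyses (including change in ER H-score) and the safety analyses do not use Appendix C. The correction is worth making because the rule is wrong as written and costs little to repair.

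**What to change.** 1. In SAP Appendix C, change the scale named in the ER row from H-score to Allred, as in protocol Table 16.
2. Name Allred in the PEPI text of SAP 2.1.3.3 and 2.4.5.3, so that the definition does not rest on a table heading alone.
3. Confirm that the central laboratory reports an Allred score for the surgical specimen. If it does not, specify before database lock how Allred is derived from the central ER reading, because the documents contain no conversion from H-score to Allred.

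If Allred is already reported, the cost is a wording correction in three places. If not, one derivation rule is added. No new samples or visits are needed.

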Appendix D Technical Details for Primary Analysis

For each treatment arm:

- the geometric mean of Ki67 proportional change (and associated 95% CI) will be computed as
$$\exp(\text{arithmetic mean of Ki67 log-proportional change})$$
- the geometric mean of Ki67 percent reduction (and associated 95% CI) will be computed as
$$1 - \text{geometric mean of proportional change (and associated 95\% CI)}$$

An analysis of covariance (ANCOVA) will be used to compare the Ki67 log-proportional changes between groups,

$$Y = a + bX + cZ$$

Where

- Y is log-proportional change from baseline to D14,
- X is the treatment group variable,
- Z is the log baseline Ki67, ie, $\log(\text{Ki67}_{\text{pre}})$,

Geometric LS-means ratio of proportional change (and associated 95% CI) between treatment arm will be calculated from the estimate (and associated 95% CI) of the difference of LS-means of the log-proportional change (and associated 95% CI) and converted by antilog transformations.

Appendix E Technical Details for ICC calculation

A mixed effect model will be fitted to the log proportional change of Ki67 measurement after 14-day treatment period:

$$y_{ij} = \mu + r_i + \delta X_{ij} + \varepsilon_{ij}$$

Where

- y_{ij} is the log proportional change from baseline to Day 14 in Ki67 measurement for the i th patient scored by the j th reader
- r_i is the random effect of the i th patient
- X_{ij} is the log baseline Ki67 value for the i th patient scored by the j th reader
- ε_{ij} is the residual error term

The random effects r_i , and ε_{ij} are assumed to be normally distributed with means of zero and variances of σ_1 and σ_2 , respectively, and to be independent of each other.

ICC is defined by $\sigma_1 / (\sigma_1 + \sigma_2)$

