2.1.3 Efficacy /pharmacodynamics endpoints

2.1.3.1 Primary endpoint(s)

The primary endpoint is the percentage reduction in Ki67 level after a 14-day treatment period compared to baseline. Ki67 level is expressed in terms of percentage of positive tumor cells tested by immunohistochemistry [IHC]) and will be recorded independently by 2 histopathologists. A single Ki67 result derived by the antilog transformation of the mean of the log of 2 reported values, will be used for calculation. The inter-reader variability in reporting Ki67 values will be

assessed during the trial, and a third adjudicator might be involved if the agreement between two Ki67 values does not meet the pre-specified criteria (see [Section 2.4.5.1.1](#)).

The primary endpoint is calculated as: $100 \times (\text{Ki67}_{\text{pre}} - \text{Ki67}_{\text{post}}) / \text{Ki67}_{\text{pre}}$, where Ki67_{pre} and $\text{Ki67}_{\text{post}}$ are used to denote the pre-treatment and post-treatment Ki67 values respectively. Since both SAR439459 and letrozole treatments intend to reduce Ki67 levels, a positive result is expected with this formula and denoting Ki67 value reduction.

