2.4 STATISTICAL METHODS

Continuous data will be summarized using the number of available data, mean, standard deviation, median, minimum and maximum for each treatment group.

Categorical and ordinal data will be summarized using the number and percentage of patients in each treatment group.

Due to early termination of enrollment, the planned sample size will not be achieved, therefore no hypothesis test will be performed on primary endpoint, confidence intervals will be estimated as two-sided and will be used for descriptive purposes only.

In summary tables, treatment arms will be presented as follows:

- SAR439859 400 mg QD (SAR439859 400 mg)
- SAR439859 200 mg QD (SAR439859 200 mg)
- Letrozole 2.5 mg QD (Letrozole 2.5 mg)

Parameters on demographics and baseline characteristics would be provided by treatment arms and overall.

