Assuming Ki67 value follows a log-normal distribution, $\log(Ki67_{post})$ and $\log(Ki67_{pre})$ will be used to denote the logs of the post-treatment and baseline values respectively. 0.1% will be added to untransformed Ki67 with 0 value to avoid the mathematical anomaly that arises because the log of zero is minus infinity. As a consequence of the assumption of a lognormal distribution, the log proportional changes ie, $\log(Ki67_{post}/Ki67_{pre})$ is also normally distributed. The log proportional change will be compared between treatment arms using an analysis of covariance (ANCOVA) model adjusting for the log Ki67 at baseline. Geometric LS-means ratio of proportional change (and associated 95% CI) between treatment arms will be calculated from the estimate (and associated 95% CI) of the difference of least squared (LS)-means of the log-proportional change (and associated 95% CI) from the ANCOVA model and converted by antilog transformations. For each treatment arm, geometric LS-means of the proportional change from baseline (and associated 95% CI) will be obtained from the ANCOVA model after conversion by antilog transformations. Geometric LS-means of percentage reduction in Ki67 (and associated 95% confidence intervals) will be calculated with 1 minus geometric LS-means of proportional change (and associated 95% confidence intervals). Hypothesis test will not be performed due to early enrollment termination.

Details of primary analysis can be found in [Appendix D](#).

Evaluation of inter-reader variability

The reproducibility of Ki67 measurements among readers will be estimated by calculating an intraclass correlation coefficient (ICC). The definition along with the statistical model for ICC estimation are provided in [Table 3](#).

Table 3 - Estimation of ICC during the trial

Notation	Definition	Model	Consistency or absolute agreement
ICC	The inter-reader agreement on log proportional change from baseline in Ki67 measurement after 14-day treatment period.	Mixed-effect model adjusted for baseline covariate, based on single rating	Absolute agreement

Mean estimations along with 95% confidence intervals will be reported for the ICC. Details of ICC estimation can be found in [Appendix E](#).

The ICC estimate will be checked at the following time-points:

- The interim analysis when 20 patients in each arm evaluable for the primary endpoint ([Section 3](#))

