- The analysis when at least 75% patients of the study completed treatment and Ki67 value available for analysis.
- The analysis when all of the patients completed treatment and Ki67 value available for analysis.

The ICC has a range of 0-1, with 1 denoting highest agreement. The ICC estimate at each analysis will be reviewed with study team, and in case a high inter-reader variability is suspected (eg, ICC <0.8), team would evaluate the necessity of inviting a third adjudicator to provide a single Ki67 result based on the readings of two assessors.

In any case, the decision as to whether adjudication will take place needs to be finalized before database lock.

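### The Appendix E reader-agreement ICC adjusts for each reader's own baseline score, so it can overstate agreement on Ki67 change and miss the example 0.8 prompt for adjudication

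*SAP*

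**What the plan says.** SAP 2.4.5.1.1, Table 3, defines the ICC as "The inter-reader agreement on log proportional change from baseline in Ki67 measurement after 14-day treatment period", of the absolute-agreement type. Its model cell reads "Mixed-effect model adjusted for baseline covariate, based on single rating". It does not say whose baseline score is meant.

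Appendix E does say. It fits y_ij = mu + r_i + delta X_ij + e_ij. Here y_ij is the log proportional change for patient i by reader j, and X_ij "is the log baseline Ki67 value for the" ith patient by the same reader j. The ICC is the patient variance over patient plus residual variance. There is no reader term.

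The ICC is checked three times, first at "The interim analysis when 20 patients in each arm evaluable for the primary endpoint". SAP 2.4.5.1.1 then states that "in case a high inter-reader variability is suspected (eg, ICC <0.8), team would evaluate the necessity of inviting a third adjudicator", and that "the decision as to whether adjudication will take place needs to be finalized before database lock". The Ki67 value analysed is a two-reader value, "derived by the antilog transformation of the mean of the log of 2 reported values" (SAP 2.1.3.1).

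**The concern.** The outcome is log post minus log baseline, and the covariate is log baseline, both from the same reader. If a reader over-scores a baseline slide by some amount, the outcome falls by that amount and the covariate rises by it. The regression sees an apparently perfect relation between the two and assigns it to the slope, so the error leaves the residual. The ICC then no longer measures absolute agreement on change, because disagreement in one of the two parts of change has been partly removed.

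This matters because the ICC is the only numeric prompt in the SAP for considering a third adjudicator. Several reported results use the baseline reading directly: the within-arm percentage reduction, the secondary endpoint of a decrease of at least 50%, and the waterfall plot.

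**Working it through.** The documents state no ICC value to reproduce, only the example threshold of 0.8.

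**Inputs from the documents**
- Planning reductions of 70% (letrozole) and 85% (each amcenestrant arm), and SD of log-fold change 1 (SAP 1.3). The planned difference reproduces: log(0.15) - log(0.30) = -1.897 + 1.204 = -0.693.
- First check at 20 per arm, so n = 60; two readers, single rating (SAP 2.4.5.1.1).

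**Assumptions (not in the documents)**
- True baseline log-SD 0.4; reader-error SDs as listed below; the planning SD of 1 applied to true change.
- Two patient structures: (A) true change independent of true baseline; (B) true post-treatment value independent of true baseline.

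**Step 1, algebra.** Let reader j's log baseline be B_i + u_ij and log post be P_i + v_ij. Then y_ij = (P_i - B_i) + v_ij - u_ij and X_ij = B_i + u_ij. After adjustment with slope delta, the within-patient error is v_ij - (1 + delta) u_ij. At delta = 0 both errors count. At delta = -1 the baseline error is gone, and y + X is simply the log post reading. With equal independent errors of 0.4 the simulated slope is -0.89 to -0.99.

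**Step 2, plain ICC of change.** Between-arm variance is 0.693² × (1/3)(2/3) = 0.107, so the variance of true change is 1 + 0.107 = 1.107.
- Errors 0.4/0.4: 1.107 / (1.107 + 0.16 + 0.16) = 0.776.
- Errors 0.5/0.5: 1.107 / (1.107 + 0.25 + 0.25) = 0.689.

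**Step 3, limit delta = -1 (ICC of the post reading alone).** The variance of true log post is 1.107 + 0.16 = 1.267 under A and 1.107 - 0.16 = 0.947 under B.
- Errors 0.4: 1.267/1.427 = 0.888 (A); 0.947/1.107 = 0.855 (B).
- Errors 0.5: 1.267/1.517 = 0.835 (A); 0.947/1.197 = 0.791 (B).

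**Step 4, REML fits at n = 60, 600 simulated trials per row.** Each arrow runs from the plain ICC to the Appendix E ICC.

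| Error SD baseline/post, correlation | A | B | Share below 0.8, plain vs Appendix E |
|---|---|---|---|
| 0.4/0.4, 0 | 0.772 → 0.881 | 0.779 → 0.855 | 65-67% vs 1-8% |
| 0.5/0.5, 0 | 0.678 → 0.824 | 0.683 → 0.788 | 97-98% vs 25-55% |
| 0.5/0.5, 0.5 | 0.811 → 0.854 | 0.811 → 0.834 | 35-38% vs 8-19% |
| 0.25/0.5, 0 | 0.775 → 0.817 | 0.776 → 0.788 | 65-66% vs 30-58% |
| 0.3/0.6, 0 | 0.707 → 0.760 | 0.703 → 0.718 | 94-95% vs 73-92% |
| 0.2/0.6, 0 | 0.730 → 0.753 | 0.729 → 0.720 | not tabulated |
| 0.3/0.6, 0.5 | 0.796 → 0.796 | 0.803 → 0.787 | 43-48% vs 49-57% |

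When post error is two to three times baseline error, the gap is about -0.02 to +0.04, with one setting at +0.05 (0.760 - 0.707).

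**Step 5, systematic disagreement (stress case).** One reader scores every baseline 0.8 log units high, with random error 0.2 elsewhere. The plain residual variance is 0.04 + 0.04 + 0.8²/2 = 0.40. The patient variance is then estimated as 1.107 + 0.08/2 - 0.40/2 = 0.947, so the plain ICC is 0.947/1.347 = 0.70. Appendix E reads 0.96 to 0.97.

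**Step 6, shared baseline.** With the two-reader mean log baseline as covariate, the baseline disagreement stays in the residual. The ICC is 0.72 to 0.77 for errors 0.4/0.4 and 0.65 to 0.70 for the offset case.

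**Step 7, what reaches the results.** With independent errors of 0.4 to 0.5, baseline error alone misclassifies 5.5 to 6.9% of patients at the 50% cut, even after averaging two readers. In the offset case the two-reader value is shifted by 0.4, so the letrozole geometric-mean reduction reads 1 - 0.30 × exp(-0.4) = 80% instead of 70%.

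**The case against.** **Adjustment is planned.** Table 3's model cell calls for baseline adjustment, and the primary ANCOVA (Appendix D) also conditions on log baseline. This stands. A reader might infer that Appendix E contradicts Table 3 merely by adjusting; the documents do not support that. The fault is narrower: the covariate is each reader's own score. The main ANCOVA uses one two-reader baseline per patient, and adjusting the ICC for that value would keep the disagreement visible (Step 6).

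**Equal errors may be a favourable case.** If log error followed binomial counting (assumed: same cell count, baseline 20 to 40%), post-treatment error would be 2.0 to 3.2 times baseline error and the gap would be small. This stands as a limit on size.

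**The stress case is partly impossible.** An offset of 0.8 is a 2.2-fold over-reading, so any true baseline above about 45% would exceed 100%. The case shows the mechanism and is not a forecast.

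**Does the prompt also fire too often?** A reader might infer this too. The reversals exist on paper, but the clear ones need a baseline log-SD near 0.8. Entry requires local Ki67 of at least 15% (Protocol 5.1), and a log-uniform spread over 15 to 100% has SD log(100/15)/√12 = 0.55. Central values can fall below 15%, so 0.8 is not excluded, but it is unlikely. The reversal also comes from adjustment shrinking patient variance, not from the own-score covariate.

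**Other safeguards exist.** SAP 2.4.5.1.3 repeats the primary analysis by reader, and SAP 2.4.5.3 adds a digital-image analysis. Both help, but the by-reader run covers only the primary analysis and is not scheduled before lock, when the adjudication decision closes.

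**Conclusion.** The concern holds in this form: Appendix E does not deliver absolute agreement on log proportional change, because the reader-specific covariate removes part of the baseline disagreement. Under equal independent errors of 0.4 to 0.5, a plain ICC of about 0.77 reads 0.85 to 0.88 and 0.68 reads 0.79 to 0.82. With correlated errors, or post-treatment error two to three times larger, the gap is small or absent. All of this rests on assumed reader errors and baseline spread; the direction usually, but not always, flatters agreement.

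The impact is modest. The 0.8 value is an example that leads to team review. The analysed value averages two readers. SAP 2.4 states "Due to early termination of enrollment, the planned sample size will not be achieved" and drops the hypothesis test. A reader might infer that the treatment comparison is compromised; the documents do not support that. Patients are randomised and the central readers are blinded, so baseline reading error should fall alike on all arms, and the between-arm ratio is largely protected. The exposed results are within-arm: the percentage reduction (shifted by a systematic offset), the endpoint of a decrease of at least 50%, and the waterfall plot.

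**What to change.** Base the 0.8 check on one of two models:
- y_ij = mu + r_i + e_ij, with no covariate, and amend the model cell of Table 3 to match; or
- to keep Table 3's adjustment, replace X_ij by one shared baseline per patient, the mean of the two readers' log baseline scores.

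In either case leave reader differences in the residual, as absolute agreement requires, and report the present Appendix E version as supplementary only.

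The cost is one model line in Appendix E and, for the first option, one table cell. No new readings or data are needed. The downside is that the ICC will often read lower and may prompt more team reviews. When weighing a low value, the team should recall that it is a single-rating figure: by Spearman-Brown, 0.68 corresponds to 2 × 0.68/1.68 = 0.81 for the two-reader mean, and 0.77 to 2 × 0.77/1.77 = 0.87.
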